1. PROTOCOL SUMMARY

Protocol Title: A Phase 2, Double-Blind, Randomized, Placebo-Controlled, Dose-Ranging, Efficacy, and Safety Study of Povorcitinib in Participants With Chronic Spontaneous Urticaria

Brief Title: A Study Evaluating the Efficacy and Safety of Povorcitinib in Adults With Chronic Spontaneous Urticaria

Protocol Number: INCB 54707-207

Objectives and Endpoints:

Table 1 presents the primary and secondary objectives and endpoints.

Table 1: Primary and Secondary Objectives and Endpoints

Objectives	Endpoints
Primary	
To evaluate the efficacy of povorcitinib in participants with CSU.	Change from baseline in the UAS7, defined as the 7-day sum of the individual, daily recorded scores for HSS and ISS, at Week 12.
Secondary	
To further evaluate the efficacy of povorcitinib in participants with CSU.	
• Proportion of participants who achieve $UAS7 \leq 6$ (controlled disease) at Week 12.• Time to first achievement of $UAS7 \leq 6$ (controlled disease) during the PC period.• Proportion of participants with $UAS7 = 0$ at Week 12.

Overall Design:

Table 2 presents the key study design elements. Further study details are presented after the table.

Table 2: Key Study Design Elements

Study Phase	Phase 2
Clinical Indication	Treatment of patients with CSU that is inadequately controlled by second-generation H1 antihistamines.
Population	Participants aged 18 to 65 years who have had a diagnosis of CSU for ≥ 3 months that is inadequately controlled by second-generation H1 antihistamines. Inadequately controlled CSU is defined as UAS7 ≥ 16 during the 7 days prior to randomization.
Number of Participants	Approximately 136 participants will be randomized 1:1:1:1 to 1 of 4 treatment groups (≈ 34 participants per group). Participants will be stratified by previous treatment of CSU with an anti-IgE biologic agent (yes or no).
Study Design	Multicenter, parallel-group, double-blind, randomized, placebo-controlled, dose-ranging study.
Estimated Duration of Study Participation	It is estimated that an individual will participate for approximately 48 weeks (11 months) as follows: 
 • Screening: up to 28 days • PC period (double-blinded): 12 weeks • EXT period (double-blinded): 24 weeks • Post-treatment follow-up: 60 days (± 7 days) after last dose of study drug
DSMB	Yes (internal)
CAC	Yes
Coordinating Principal Investigator	[name]. [name]

Treatment Groups and Duration:

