The study will enroll approximately 136 participants in a 1:1:1:1 randomization ratio, stratified by previous anti-IgE biologic use, into 1 of 4 treatment groups during the double-blind, PC period (12 weeks).

After completing the 12-week PC period, participants will enter the 24-week EXT period. During the EXT period, the participants initially randomized to povorcitinib will continue taking povorcitinib at the same dose regimen (ie, povorcitinib 15, 45, or 75 mg QD). The participants initially randomized to placebo at baseline will receive povorcitinib 15, 45, or 75 mg QD.

Participants will receive study drug until completion of the 36-week treatment period or until 1 of the criteria for study treatment discontinuation are met. Participants will return for a follow-up visit approximately 60 days after their last dose of study drug.

All participants are required to maintain a background therapy of a stable dose of second-generation H1 antihistamine (SOC) during the study (ie, from screening through follow-up). The SOC will be determined by the investigator. Further doses of second-generation H1 antihistamine may be used as rescue medication to treat worsening CSU symptoms at any time during the study. A 1-time, short course (maximum duration of 7 days) of glucocorticosteroids may be used as rescue medication after Week 4 in the case of severe exacerbation.

Figure 1 presents the study design schema, and Table 3 presents the SoA. Adherence to the study design requirements, including those specified in the SoA, is essential and required for study conduct.

Figure 1: Study Design Schema

[figure not shown]

Table 3: Schedule of Activities

Visit Day (Range)	Screening	PC Period (12 Weeks)				EXT Period (24 Weeks)						Post-Treatment Follow-Up	Notes and Protocol Section	
	Days -28 to -1	Baseline Day 1	Week 4 (± 3 d)	Week 8 (± 3 d)	Week 12/ EOT1 (or ET1) (± 3 d)	Week 16 (± 3 d)	Week 20 (± 3 d)	Week 24 (± 3 d)	Week 28 (± 3 d)	Week 32 (± 3 d)	Week 36/ EOT2 (or ET2) (± 3 d)	Week 44/ EOS (± 7 d)		
Administrative procedures														
Informed consent	X													Section 8.1.1
Inclusion/exclusion criteria	X	X												Section 5
Demographic data, general medical history, and CSU medical and treatment history	X													Section 8.1.7
Previous use of anti-IgE biologic	X													
Prior/concomitant medications	X	X	X	X	X	X	X	X	X	X	X	X	X	Section 6.7
Rescue medication use		X	X	X	X	X	X	X	X	X	X	X	X	Section 6.7.3

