6.5.1. Compliance With Povorcitinib/Placebo

Compliance with study drug will be calculated by the sponsor based on the drug accountability (eg, tablet counts) documented by the site staff and monitored by the sponsor/designee. Participants will be instructed to bring all unused study drugs with them to the study visits in order for site personnel to conduct tablet counts to assess study drug accountability.

Compliance with study drug will be calculated for the PC and EXT periods based on the following:

Within the PC period:

- The first dose will occur on Day 1 (baseline).
- The last dose will occur on the day of the Week 12 visit or the day of the last study drug administration known to the investigator (or designee) as reported in the EDC for participants who prematurely discontinue study treatment or are lost to follow-up.

Within the EXT period:

- The first dose will occur the day after the Week 12 visit.
- The last dose will occur on the day of the Week 36 visit or the day of the last study drug administration known to the investigator (or designee) as reported in the EDC for participants who prematurely discontinue study treatment or are lost to follow-up.

Participants' compliance must be within 80% to 120% assessed at each study visit by the investigator (or designee). If outside of this range, it will be considered a Protocol deviation. Participants consistently noncompliant with the study drug may be withdrawn from the study. The decision on withdrawal will be made by the investigator after consultation with the sponsor, and relevant correspondence will be archived in the site study file.

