8.3.1. Adverse Events

Adverse events will be monitored from the time the participant signs the ICF until at least 60 days after the last dose of study drug. Adverse events for randomized participants that begin or worsen after informed consent should be recorded on the Adverse Events Form in the eCRF regardless of the assumption of a causal relationship with the study drug. Conditions that were already present at the time of informed consent should be recorded on the Medical History Form in the eCRF. Adverse events (including laboratory abnormalities that constitute AEs) should be described using a diagnosis whenever possible rather than by individual underlying signs and symptoms.

Adverse events will be reported by the participant (or, when appropriate, by a caregiver, surrogate, or the participant's legally authorized representative). The investigator and any qualified designees are responsible for detecting, documenting, and recording events that meet the definition of an AE or SAE and remain responsible for following up on AEs that are serious, that are considered related to the study drug procedures, or that caused the participant to discontinue the study drug. Care will be taken not to introduce bias when detecting AEs and/or SAEs. Open-ended and nonleading verbal questioning of the participant, such as "How are you feeling?", is the preferred method to inquire about AE occurrences. Adverse events may also be detected when they are volunteered by the participant during the screening process or between visits or through physical examinations, laboratory tests, or other assessments. The definition, reporting, and recording requirements for AEs are described in Section [9](#).

All SAEs will be reported to the sponsor or designee within 24 hours. The investigator will submit any updated SAE data to the sponsor within 24 hours of it being available.

After the initial AE/SAE report, the investigator is required to proactively follow each participant at subsequent visits/contacts. All AEs and SAEs (as defined in Section [9.2](#)) will be followed until resolution, stabilization, the event is otherwise explained, or the participant is lost to follow-up (as defined in Section [7.3](#)).

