8.8. Follow-Up

8.8.1. Post-Treatment Follow-Up

The post-treatment follow-up period is the interval between the Week 36 visit and the scheduled follow-up visit, which should occur 60 (\pm 7) days after the Week 36 visit (or after the last dose of study drug if the Week 36 visit was not performed). Adverse events and SAEs must be reported up until 1) at least 60 days after the last dose of study drug or 2) until toxicities resolve, return to baseline, or are deemed irreversible, whichever is longer. Reasonable efforts should be made to have the participant return for the post-treatment follow-up visit and report any AEs that may occur during this period. If the participant cannot return to the site for the post-treatment follow-up visit, then the participant should be contacted by telephone for assessment of AEs and SAEs and sites should properly document this contact in the source.

9. ADVERSE EVENTS: DEFINITIONS AND PROCEDURES FOR RECORDING, EVALUATING, FOLLOW-UP, AND REPORTING

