9.4. Reporting of Serious Adverse Events

Regardless of suspected causality (eg, relationship to study drug or study procedure[s]), all SAEs occurring after the participant has signed the ICF through at least 60 days after the last dose of study drug must be reported to the sponsor (or designee) immediately, without undue delay but not later than within 24 hours of obtaining knowledge of its occurrence unless otherwise specified by the Protocol. The investigator will submit any updated SAE data to the sponsor (or designee) immediately, without undue delay but not later than within 24 hours of it being available.

Investigators are not obligated to actively seek SAE information after the post-treatment follow-up visit or more than 60 days after the last dose of study drug. If the investigator learns of any SAE, including death, at any time during this period, and they consider the event to be reasonably related to the study drug or study participation, then the investigator must notify the sponsor (or designee) within 24 hours of becoming aware of the event.

After the initial AE/SAE report, the investigator is required to proactively follow each participant at subsequent visits/contacts. All SAEs and AESIs (as defined in Section 9.6.1) will be followed until resolution, stabilization, the event is otherwise explained, or the participant is lost to follow-up (as defined in Section 7.3).

Prompt notification by the investigator to the sponsor regarding an SAE is essential so that legal obligations and ethical responsibilities for the safety of participants and the safety of a study drug under clinical investigation are met.

If the SAE is not documented in the RSI of the IB for the study drug (new occurrence) and is thought to be related to the study drug, the sponsor or its designee may urgently require further

information from the investigator for expedited reporting to health authorities. The sponsor or its designee may need to issue an Investigator Notification to inform all investigators involved in any study with the same drug that this SAE has been reported. Suspected unexpected serious adverse reactions will be collected and reported to the competent authorities and relevant ethics committees in accordance with Directive 2001/20/EC or as per national regulatory requirements in participating countries.

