10.4.3. Safety Analyses

Safety analyses will be conducted for the safety population. Adverse events will be coded by the MedDRA dictionary, and TEAEs (ie, AEs reported for the first time or worsening of a pre-existing event after first dose of study drug and until 60 days after the last dose of study drug) will be tabulated by preferred term and system organ class for all events, related events, and events of Grade 3 or higher. The Protocol-defined ECIs and AESIs will be tabulated by preferred term and Protocol-defined categories for all events. Quantitative safety variables (eg, laboratory values, vital signs) and their changes from baseline will be summarized with descriptive statistics. Clinically notable abnormal values will be flagged and tabulated based on predefined criteria.

The subset of AEs considered by the investigator to have a relationship to study drug will be considered to be treatment-related AEs. If the investigator does not specify the relationship of the AE to study drug, then the AE will be considered treatment-related. The incidence of AEs and treatment-related AEs will be tabulated.

The clinical laboratory data will be analyzed using summary statistics; no formal treatment group comparisons are planned. In addition, distributions of key laboratory parameters may be plotted over time; these values will also be classified into CTCAE v5.0 toxicity grades and tabulated. Descriptive statistics and mean change from baseline will be determined for vital signs at each assessment time. Vital sign results will be reviewed for clinically notable abnormalities. Descriptive statistics and mean change from baseline will be determined for each ECG parameter at each assessment time.

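### The last scheduled adverse-event contact is timed two ways, and both timings allow it before the protocol's 60-day collection period ends

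*Protocol*

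**What the plan says.** **How long events are to be collected.** Protocol 8.3.1: "Adverse events will be monitored from the time the participant signs the ICF until at least 60 days after the last dose of study drug". Protocol 8.8.1: "Adverse events and SAEs must be reported up until 1) at least 60 days after the last dose of study drug", or longer if toxicities have not resolved. The opening of 9.4 requires all SAEs, whatever their suspected cause, through at least 60 days after the last dose. Protocol 10.4.3 counts treatment-emergent events "after first dose of study drug and until 60 days after the last dose of study drug".

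**When the last dose is taken.** For completers, 6.5.1 says "The last dose will occur on the day of the Week 36 visit".

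**When the last planned contact occurs.** The final adverse-event assessment in Table 3 is in the Week 44/EOS column, which has a window of 7 days either side. Section 6.7.3 also labels the post-treatment follow-up period as Week 36 to Week 44, and the eDiary row of Table 3 runs through Week 44. Table 2 says "Post-treatment follow-up: 60 days (± 7 days) after last dose of study drug", and 4.2 agrees. Section 8.8.1 gives the same 60 ± 7 days, counted from the Week 36 visit, or from the last dose if that visit was not done.

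**What happens after that contact.** No later contact is scheduled. The telephone call in 8.8.1 is for participants who cannot return for the visit. Section 9.4 says "Investigators are not obligated to actively seek SAE information after the post-treatment follow-up visit or more than 60 days after the last dose". Section 7.1.2 follows participants who stop treatment until the follow-up visit or until drug-related toxicities settle, whichever is longest, and does not mention Day 60.

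**The concern.** There are two separate problems. The first is that the EOS visit has two target days and two windows, so sites working from different parts of the protocol will book it differently. The second is that both windows open before Day 60. A site can therefore follow the schedule exactly and have its last planned adverse-event enquiry before the stated collection period is over.

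Section 9.4 makes the second problem harder to dismiss. It joins the visit and the 60-day limit with *or*, so the visit alone may be taken to end active SAE seeking. Its next sentence then asks only for SAEs thought reasonably related. For a participant seen before Day 60, that sits awkwardly with the opening of 9.4, which wants every SAE to at least Day 60 regardless of cause.

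At stake is complete and uniform safety capture in the last days after stopping a JAK inhibitor. Protocol Table 4 lists serious infection and thromboembolic events among the risks to be monitored. Events in those days that nobody asks about will be recorded only if the participant volunteers them or the site learns of them in some other way.

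**Working it through.** This is calendar arithmetic. Days are counted from the Week 36 visit, which for completers is also the day of the last dose (6.5.1).

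**1. The plan's own duration figure.** Table 2 estimates about 48 weeks (11 months) of participation. Adding screening, placebo-controlled period, extension and follow-up:
- with the Week 44 label: 28 + 84 + 168 + 56 = 336 days; 336 / 7 = 48.0 weeks
- with the 60-day text: 28 + 84 + 168 + 60 = 340 days; 340 / 7 = 48.6 weeks

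Both fit an approximate 48 weeks, so this figure does not settle which schedule was intended.

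**2. Nominal visit day.**
- Table 3: (44 − 36) × 7 = 56 days, which is 60 − 56 = 4 days short
- Table 2, 4.2 and 8.8.1: 60 days, no shortfall

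**3. Windows and largest shortfall.**
- Table 3: 56 ± 7 = Days 49 to 63; the earliest visit is 60 − 49 = 11 days short
- Table 2, 4.2 and 8.8.1: 60 ± 7 = Days 53 to 67; the earliest visit is 60 − 53 = 7 days short

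**4. Permitted days that fall before Day 60.** Each window contains 15 days.
- Table 3: Days 49 to 59, 11 of 15 (73%)
- Table 2, 4.2 and 8.8.1: Days 53 to 59, 7 of 15 (47%)

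These are shares of permitted days. They become shares of participants only if visits are spread evenly over the window, which no document supports. With other attendance patterns the share of participants seen early could be anything from none to all.

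**5. Sensitivity to the anchor.** If both Table 3 windows are assumed to be counted from Day 1, and Week 36 was 3 days late while Week 44 was 7 days early, the interval is 56 − 3 − 7 = 46 days, 14 short. In the opposite case it is 56 + 3 + 7 = 66 days, with no shortfall. Section 8.8.1 counts from the Week 36 visit, so the 14-day figure depends on this assumption.

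**6. Participants who stop early.** Section 8.8.1 times their visit from the last dose, giving Days 53 to 67 and a largest shortfall of 7 days. The Week 44 figures do not carry over to them.

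**The case against.** The strongest answer is that the 60-day duty is stated several times and no passage withdraws it. Sections 8.3.1, 8.8.1 and the opening of 9.4 all run to at least Day 60, toxicities still unresolved are followed longer, and unscheduled visits are allowed. The protocol elsewhere describes the visit as about 60 days after the last dose, and Week 44 may be a rounded label. The two windows overlap on Days 53 to 63, so a site can satisfy both, and a visit on Days 60 to 63 leaves no gap. The primary and secondary endpoints end by Week 12 and are untouched, and the final analysis makes no statistical comparison with placebo.

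All of that stands, and it rules out several stronger readings that a reader might infer:

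- *Sites stop asking about adverse events on Day 56.* No passage says so. The release in 9.4 concerns active seeking of SAEs only.
- *Every participant is affected.* Only those seen before Day 60 lose solicited time, and not all of the approximately 136 randomized will reach the visit.
- *The shortfall is 14 days.* That needs the Day 1 anchor set out in the working.
- *The tables will present a 60-day safety period that was not observed.* Protocol 10.4.3 uses 60 days, but SAP 9.2.1 does not. Its general definition runs to 30 days after the last dose, its extension-period definition to EOT2, and its overall povorcitinib-only definition to EOS.

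What the objection does not supply is a planned contact on or after Day 60 for a participant seen earlier.

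**Conclusion.** The point holds as a scheduling inconsistency with a gap in planned solicitation. Whichever schedule governs, a compliant EOS visit may precede Day 60. For completers the gap is 4 days at the nominal Table 3 date, up to 11 days under Table 3 and up to 7 days under 8.8.1. It does not remove the duty to report and does not touch the efficacy analyses.

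The conclusion rests on two readings of the text: that the last dose falls on the Week 36 visit day for completers, as 6.5.1 states, and that no contact beyond those in Table 3 and 8.8.1 is planned. How many participants would be seen early cannot be derived from the documents.

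**What to change.** 1. Use one EOS definition, anchored to the last dose, in Table 2, Table 3, 4.2 and 8.8.1. Reconcile the other Week 44 references with it: the eDiary row of Table 3 and the follow-up period label in 6.7.3.
2. Either open the window no earlier than Day 60 (for example Day 60, +7/−0), or require a telephone AE/SAE contact on or after Day 60 whenever the visit takes place earlier.
3. Reword 9.4 and 7.1.2 so that the visit alone does not end solicitation before Day 60.
4. Separately, reconcile the treatment-emergent windows in SAP 9.2.1 (30 days, EOT2, EOS) with the 60 days in Protocol 10.4.3.

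**Cost.** Wording changes in the sections named, plus either a narrower visit window or one short call for early attenders. No assessment is added beyond that call. The call would pick up clinical events but not laboratory abnormalities. If late laboratory values matter, moving the window is the better option.

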9.1. Definition of Adverse Event

Adverse Event Definition

• An AE is any untoward medical occurrence associated with the use of a drug in humans, whether or not it is considered drug-related.• An AE can therefore be any unfavorable or unintended sign (including an abnormal laboratory finding), symptom, or disease (new or exacerbated) temporally associated with the use of study drug.
Additional Guidance for Events Meeting the Adverse Event Definition

• Any safety assessments (eg, ECG, vital signs measurements), including those that worsen from baseline, considered clinically significant in the medical and scientific judgment of the investigator (ie, not related to disease progression) are to be reported as an AE.• Abnormal laboratory test results are to be reported as an AE if they are considered clinically meaningful, induce clinical signs or symptoms, require concomitant therapy, or require changes in study drug. Whenever possible, a diagnosis (eg, anemia, thrombocytopenia) should be recorded in the eCRF rather than the abnormal laboratory test result (eg, low hemoglobin, platelet count decreased).• Exacerbation of a chronic or intermittent pre-existing condition/disease, including either an increase in the frequency and/or intensity of the condition, is to be reported as an AE.• New conditions detected or diagnosed after the start of study drug administration are to be reported as an AE.• New signs and/or symptoms due to the study disease that develop after the first dose of study drug are to be reported as an AE.• Signs, symptoms, or the clinical sequelae of a suspected drug-drug interaction are to be reported as an AE.• Signs and/or symptoms from dose administration errors of a study drug (eg, overdose) or a concomitant medication are to be reported as an AE.• "Lack of efficacy," "disease progression," or "failure of expected pharmacological action" will not be reported as an AE or SAE. Such instances will be captured in the efficacy assessments. However, the signs, symptoms, and/or clinical sequelae resulting from lack of efficacy will be reported as AE or SAE if they fulfil the definition of an AE or SAE. If judged by the investigator more severe than expected for the participant's condition, any clinically significant abnormal laboratory findings or other abnormal safety assessments that are associated with the underlying disease can be reported as an AE or SAE. And if judged by the investigator more severe than expected for the participant's condition, the disease/disorder being studied or its expected progression, signs, or symptoms can be reported as an AE or SAE.• A condition that leads to a medical or surgical procedure (eg, endoscopy, appendectomy) will be reported as an AE if it occurs after obtaining informed consent. If the condition is present before entering the study, then it should be captured as medical history.• Pre-existing diseases, pre-existing conditions, or new conditions with expected fluctuations in signs or symptoms should be reported as an AE only if the investigator judges the fluctuation to have worsened more than expected during study participation.

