### 9.2. Adverse Events

#### 9.2.1. Adverse Event Definitions

A TEAE is any AE either reported for the first time or worsening of a pre-existing event after the first dose of study drug and up to 30 days after the last dose of study drug. Analysis of AEs will be limited to TEAEs, but data listings will include all AEs regardless of their timing in relation to study drug administration. For purposes of analysis, all AEs will be considered TEAEs unless the AE can unequivocally be defined as not treatment emergent.

A TEAE during the PC period is any AE with a start time after the first dose of study drug during the PC period and until the end of the safety follow-up or prior to the first dose during the EXT period for participants who entered the EXT period.

A TEAE during the EXT period is any AE with a start time after the first dose of study drug during the EXT period and until the end of the EOT2.

For participants who received only povorcitinib 15, 45, or 75 mg during the overall period, a TEAE is any AE with a start time after the first dose of study drug during the PC period and until the EOS.

Adverse events will be tabulated by MedDRA PT and SOC. Severity of AEs will be graded using the National Cancer Institute CTCAE v5.0. The CTCAE reporting guidelines and grading details are available on the Cancer Therapy Evaluation Program website.

The subset of AEs considered by the investigator to be related to study drug will be considered to be treatment-related AEs. If the investigator does not specify the relationship of the AE to study drug, the AE will be considered to be treatment related. The incidence of AEs and treatment-related AEs will be tabulated. Serious treatment-related TEAEs will also be tabulated.

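### Protocol 9.1 gives conflicting, unranked rules for reporting ordinary CSU worsening as an AE, so pooled TEAE rates depend on the rule followed and can understate a drug excess

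*Protocol*

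**What the plan says.** Protocol 9.1 defines an AE broadly enough to take in a "symptom, or disease (new or exacerbated) temporally associated with the use of study drug". Four bullets in the guidance below that definition bear on CSU:

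- **Exacerbation.** "Exacerbation of a chronic or intermittent pre-existing condition/disease, including either an increase in the frequency and/or intensity of the condition, is to be reported". There is no severity threshold and no exception for the study disease.
- **New features.** "New signs and/or symptoms due to the study disease that develop after the first dose of study drug are to be reported as an AE". This covers new signs or symptoms, not a rise in those already present.
- **Lack of efficacy.** Lack of efficacy, disease progression and failure of the expected drug action are kept out of AE reporting: "Such instances will be captured in the efficacy assessments". The same bullet then brings the resulting signs and symptoms back in if they meet the AE definition. It ends by saying that the study disease can be reported when the investigator judges it more severe than expected.
- **Expected fluctuation.** A condition with expected fluctuations "should be reported as an AE only if the investigator judges the fluctuation to have worsened more than expected during study participation".

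No text ranks these bullets or says what is expected for CSU. SAP 9.2.1 then takes in whatever is recorded: "A TEAE is any AE either reported for the first time or worsening of a pre-existing event after the first dose of study drug". Neither that definition nor the one in Protocol 10.4.3 excludes study-disease events. SAP 9.2.2 plans an overall summary (any TEAE, Grade 3 or higher, treatment-related, requiring concomitant medication, and others) and tables by system organ class and preferred term. No planned summary leaves CSU terms out.

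**The concern.** Every participant enters with CSU (Protocol 5.1), and the disease fluctuates. A flare within the expected range has to be reported under the exacerbation bullet and must not be reported under the fluctuation bullet. A flare worse than expected is mandatory under the first and only optional under the closing sentence of the lack-of-efficacy bullet.

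This matters because CSU worsening is the reverse of efficacy. Protocol 2.3, Table 4 itself links aggravation of CSU to insufficient efficacy. If the drug works, flares will be commoner on placebo. A rule that counts them adds participants mainly to the placebo numerator of pooled rates, which can shrink a real excess of other events on povorcitinib. The any-TEAE rate is the most exposed. The rate of TEAEs requiring concomitant medication may be too, because added antihistamine is allowed as rescue throughout treatment (Protocol 6.7.3). CSU worsening has no AESI or ECI category of its own, so ordinary AE reporting is its only route into the safety tables.

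**Working it through.** **1. The rules side by side**

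| Protocol 9.1 rule | Within-expected CSU flare | Worse-than-expected CSU flare |
|---|---|---|
| Exacerbation bullet | report | report |
| New-features bullet | not reached unless the sign is new | not reached unless the sign is new |
| Lack-of-efficacy bullet | kept out as a label; symptoms return if they meet the AE definition | may be reported |
| Fluctuation bullet | do not report | report |

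The first and last rows contradict each other in the middle column. The third row does not settle it, because the AE definition it points back to already includes an exacerbated disease.

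**2. The plan's own figure**

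The documents state no TEAE rate and no CSU-worsening rate. The inputs used below (changes of -8 and -17, SD 13, 34 per group) come from Protocol 10.1, which states a minimum power of 0.85. Recomputing MCP-Mod with the six candidate shapes at doses 0, 15, 45 and 75 mg, optimal contrasts and a one-sided 0.025 multivariate-t critical value of about 2.19 gives 0.846 to 0.848. The stated figure reproduces.

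**3. How much commoner worsening is on placebo**

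With normal changes, P(rise above t) = 1 - Φ((t - mean)/SD).

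- Any rise (t = 0): placebo 1 - Φ(8/13) = 26.9%; 75 mg 1 - Φ(17/13) = 9.5%. That is about 9 and 3 of 34, a ratio of 2.8.
- Above 5 points: 1 - Φ(13/13) = 15.9%; 1 - Φ(22/13) = 4.5%.
- Above 9.5 points: 1 - Φ(17.5/13) = 8.9%; 1 - Φ(26.5/13) = 2.1%.

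**4. Effect on the any-TEAE rate**

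Let a be the other-cause TEAE rate (an assumption), w the probability of a rise and q the share of rises recorded as AEs. With independence, the rate is 1 - (1 - a)(1 - qw). Differences below use unrounded values.

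Other-cause rates of 50% on placebo and 60% on drug, a true excess of 10 points:

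- All rises recorded: 1 - 0.50 × 0.731 = 63.5% against 1 - 0.40 × 0.905 = 63.8%; excess 0.4 points.
- Only rises above 5 points: 57.9% against 61.8%; excess 3.9.
- Only rises above 9.5 points: 54.5% against 60.8%; excess 6.4.
- A quarter of all rises: 1 - 0.50 × (1 - 0.25 × 0.269) = 53.4% against 1 - 0.40 × (1 - 0.25 × 0.095) = 61.0%; excess 7.6.

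Other assumed pairs:

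- 40% and 55% (true excess 15.0): 12.0, 9.1, 6.1 and 3.1 points when 25%, 50%, 75% and 100% of rises are recorded.
- 40% and 50%, all rises recorded: -1.4 points.
- 30% and 40%, all rises recorded: -3.1 points.

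**5. The excess that would be cancelled exactly**

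This is (1 - a)(w_placebo - w_drug)/(1 - w_drug). For placebo other-cause rates of 30% to 60%, it runs from 13.4 down to 7.7 points if all rises are recorded, and from 4.9 down to 2.8 if only rises above 9.5 points are.

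**The case against.** Several arguments limit the point, and most of them stand.

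- **The section can be read as workable.** If the specific rule overrides the general, expected fluctuation is not an AE and worse-than-expected CSU is. That is sensible, but nothing in 9.1 tells a site to read it so. Protocol 9.3 refers to eCRF guidelines that may already give the rule; they are not among the documents.
- **A reader might infer that 9.1 forbids reporting CSU worsening.** It does not. The lack-of-efficacy bullet bars labels and readmits symptoms that meet the definition. Only within-expected fluctuation is excluded outright.
- **A reader might infer that the SAP cannot show CSU events apart.** It can. The tables by system organ class and preferred term in SAP 9.2.2 give urticaria and pruritus terms their own rows by arm, and unrelated AESI categories such as herpes zoster or thrombosis are not diluted. What those rows cannot give is a pooled rate without CSU: one participant can have several terms, so subtracting a row also removes people who had another TEAE.
- **The arithmetic is illustrative.** The other-cause rates are invented. The model turns every Week 12 rise into an AE, although AEs come largely from participant reports and open-ended questions (Protocol 8.3.1), not the diary score. It ignores the 0 to 42 bounds and the entry threshold of 16, and Week 12 status is not the same as any flare over 12 weeks.
- **Precision is low anyway.** At 34 per arm, with rates of 50% and 60%, the standard error of the difference is √((0.25 + 0.24)/34) = 12 points, so a 10-point excess could not be resolved in any case. That limits inference, but does not justify a systematic shift in the estimate.
- **Site habits are not tied to arm.** Randomization and blinding see to that, so the documents do not support saying that the arms cannot be compared. The shift comes from the true difference in worsening, and uniform reporting would not remove it.

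**Conclusion.** The point holds in a limited form. Protocol 9.1 contains a real, unranked conflict over within-expected CSU worsening, and treats worse-than-expected CSU as mandatory in one bullet and optional in another. Under the plan's own efficacy assumptions, worsening at Week 12 is about 2.8 times as common on placebo as on 75 mg, so counting it pulls pooled participant-level comparisons in the drug's favour. In the 50%/60% example the 10-point excess falls to between 7.6 and 0.4 points, depending on the share and size of rises recorded. Reversal appears only with some assumed rates and complete recording.

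The direction rests on the sample-size assumptions. The size rests on assumed other-cause rates, normality and independence. A general claim that drug harms would be hidden goes further than the documents allow, because preferred-term rows and AESI tables remain readable. No effect was calculated for the treatment-related, Grade 3 or higher, or discontinuation summaries.

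**What to change.** Two changes:

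1. **Protocol 9.1, or the eCRF completion guideline.** The sponsor should reconcile the bullets into one stated rule for reporting CSU signs and symptoms, and say how the exacerbation and new-features bullets apply to the study disease. SAE criteria should not serve as the trigger: Protocol 9.2 says that an event that is not an AE cannot be an SAE, so the test would be circular.
2. **SAP 9.2.2.** Beside the unchanged all-TEAE tables, add one overall TEAE summary by arm that excludes a prespecified list of CSU-worsening preferred terms. It helps even if sites have already reported under different bullets. The same figures could be derived later from the AE listing, but the term list would then be chosen with the arms known.

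The cost is one paragraph, one extra table and a short term list to maintain. The added summary could also drop drug-induced urticaria or hypersensitivity coded to the same terms. Those events stay visible in the all-TEAE tables, which is why the new summary should supplement them and not replace them.
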